Aim 3: Examine outcome patterns suggesting the efficacy of the HCT Symptoms and Steps protocol for improving physical disability and other outcomes compared to an HCT Education group. H3: Between-group effect sizes will be used to evaluate patterns suggesting intervention efficacy on measures of physical disability (self-report, 6-min walk test), pain, fatigue, distress, physical activity (daily steps), and self-efficacy for symptom management.

Confirmed hypotheses would provide the first demonstration of the feasibility, acceptability, and positive impact of a hybrid in-person and mHealth coping skills training and activity coaching intervention that reduces physical disability by concurrently and synergistically decreasing symptom burden and increasing physical activity. This project has the potential to lead to future research (R01) that can redesign existing modes of behavioral intervention delivery, improve continuity and coordination of care, and ultimately enhance patient outcomes.

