We propose a novel intervention protocol that uses a hybrid in-person and mHealth intervention delivery model. The use of mHealth technology to deliver the proposed intervention is likely to be more effective than traditional interventions delivered in-person only, improving patient access to the intervention by decreasing burden. The NIH recently stated that the future of patient care should use a hybrid model of face-to-face contact integrated with remote strategies to provide balance between technology and the "human touch." The proposed innovative intervention addresses these recommendations (i.e., inperson and mHealth strategies). We have piloted hybrid work and the proposed project is a natural extension as we increase face-to-face contact, increase mHealth technology, and address shortcomings of the previous protocol (we now address pain, fatigue and distress, and incorporate activity coaching). Our past protocol included 1 in-person session at the hospital between patient and therapist, which led to development of a successful working relationship and integration of the intervention with the patient's medical care. 31 Then, once the patient returned home, 5 sessions were conducted via video-conferencing. This bridge between hospitalization and home maintained continuity of care. This work demonstrated that a mixed delivery modality fostered a strong patient-therapist relationship that likely increased feasibility, acceptability, and efficacy of the intervention. Further, our experience with mHealth technology suggests video-conferencing is human touch as it mirrors inperson sessions and is interactive and personal. Traditional coping skills training interventions have been delivered almost exclusively in-person in major medical centers. For HCT patients, travel is burdensome due to significant symptom burden and strict activity restrictions. Distance from medical centers is a concern for several communities in the US and mHealth interventions can increase access to care. An intervention that begins inperson immediately following transplant and continues via mHealth technology increases access by reducing travel barriers for a cancer population that experiences significant burden.

\*Due to COVID-19, we propose a **temporary** amendment. Session 1-3 will now be conducted via telephone or video-conferencing, the same way as the approved session 4-7.

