Methodological Features. This protocol has several important methodological features. First, we will combine symptom management and activity coaching to address the multiple recovery challenges faced by HCT patients. Second, we will use in-person and videoconferencing sessions to bridge hospitalization and home. The initial HCT Symptoms and Steps coping skill (1) and activity coaching (2) sessions will be in-person in the hospital which provides several benefits including: integration of HCT Symptoms and Steps into patients' medical care; facilitation of a relationship between therapist and patient; and, establishment of care that bridges hospitalization and home. All sessions following the initial in-person sessions will be delivered to the patient in his/her home through videoconferencing. The use of video-conferencing (vs. in-person or phone) is likely to provide important advantages. A) HCT patients often live many miles from the hospital and are advised against extended travel thus video-conferencing will increase intervention access. B) Empirical work suggests educational and psychosocial content is better communicated through video-conferencing than by phone. C) Video-conferencing may enhance factors suggested by social cognitive theory to impact self-efficacy for symptom management: mast ery, enhanced by practice/feedback in the home environment; vicarious learning, enhanced by therapist and video clip modeling; verbal encouragement, personalized to the patient's home skills practice; and, observation of and addressing negative physiological and affective responses to skills use in the patient's practice environment. Third, a mobile app will provide HCT Symptoms and Steps participants with accessible coping skill content (audio and video), data syncing of daily steps from their wireless activity tracker, daily assessment of symptoms and activity, and real-time personalized feedback (push notification) based on symptoms and steps. The mobile app will be accessible on study iPhones and/or personal tablets/smart phones. Fourth, we have incorporated an objective assessment of physical disability (6-min walk test).

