Randomized Controlled Trial. We will use a small RCT to assess the feasibility, acceptability, and outcome patterns suggesting efficacy of a HCT Coping Skills Training for Symptom Management and Daily Steps (HCT Symptoms and Steps) protocol. This study will be conducted in the ABMT Clinic with 40 HCT patients. Following consent (consent process detailed below), participants will be randomly assigned in equal allocation to one of two conditions: 1) HCT Symptoms and Steps or 2) HCT Education. HCT Symptoms and Steps will provide patients with cognitive behavioral coping skills training and activity coaching sessions to enhance their ability to manage symptoms that interfere with activity. All participants will receive a wireless activity tracker (Fitbit) to track steps; Fitbits will not be returned, participants will keep their Fitbit. All participants who do not have a smart phone will be lent one (iPhone) equipped with Internet access to access the mHealth features: video-conferencing, coping skill content, activity tracker syncing, daily symptoms assessment, and personalized feedback (via push notification) based on symptom and step data. HCT Education will only have access to activity tracker syncing and daily symptoms assessment. HCT education participants will be encouraged to download the Transplant (HCT) Guidelines mobile app that is free of charge. The Transplant Guidelines app is developed by the National Marrow Donor Program and designed for HCT patients with a focus on treatment guidelines for patients before and after transplant. The Transplant Guidelines App provides recommended annual check-up guidelines and timing and contains helpful information, checklists and reminders for patients who have had a blood or marrow transplant. App content also includes cancer education, information about health and well-being, cancer treatment guidelines specific to HCT patients, and what to expect at follow-up visits. App features allow participants to use a GvHD symptom checker to help identify early signs of GvHD and make notes, e-mail guidelines and symptom checker results to self, and set reminders for appointments, medications, and exercise. All participants will complete 2 assessments: pretreatment and post-treatment. We will recruit 10 patients per quarter (3-4/month) to complete the recruitment goal of 40. Participants will receive \$20 for completing each assessment. Th erapist Training. Coping skills training sessions will be delivered by a doctoral level psychologist with experience delivering cognitive behavioral interventions. Activity coaching sessions will be delivered by an OT with expertise working with HCT patients. Treatment strategies will be taught through didactic instruction, audio-/video-recorded illustration of techniques, and role-play. Procedures to Ensure Consistency of Treatment. To ensure consistency with the intervention protocol: 1) therapists will follow a treatment manual, 2) weekly supervision will occur, 3) sessions will be audio-recorded and reviewed during supervision and feedback provided, and 4) ratings of treatment adherence and competence will be conducted.

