There are few risks linked to participating in in-clinic activity coaching sessions with an occupational therapist that center on daily steps. The activity coaching component of the intervention is being designed in part by hematology oncology providers and an occupational therapist who specializes in working with hematology oncology patients. Further, the activity coaching sessions will be led by a senior level occupational therapist at Duke University Hospital who holds a lymphedema therapist certification and specializes in working with hematopoietic stem cell transplant (HCT) patients pre- and post-transplant. The activity coaching component of the intervention is consistent with clinical recommendations for activity post-transplant and will be modified based on the patient participant's level of functioning. We will obtain physician clearance for activity prior to initiating the intervention sessions. While we do not anticipate any adverse events, we have developed a protocol to protect against and track adverse events related to exercise injuries /falls, lymphedema flares, hypotension or hypoglycemia, and cardiovascular events.

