The risks associated with this study are minimal and rare. During the assessments, participants will be asked to complete a walking test. The 6 minute walk test will be conducted in a hallway at the Duke ABMT Clinic or in a hallway in our research lab office space at the Pain Prevention and Treatment Research Program located in Erwin Square ([name]). Study staff (e.g., CRC, Occupational Therapist) will complete the 6 minute walk test. The 6 minute walk test is optional for participants; if a patient declines, we will not conduct the test. Further, we will check patients' blood pressure prior to conducting the 6 minute walk test and if any of the following contraindications are present, we will not conduct the test: (1) unstable angina during the previous month, (2) myocardial infarction during the previous month, (3) resting heart rate >120, (4) systolic blood pressure >180 mm Hg, (5) Diastolic blood pressure >100 mm Hg. There are some risks associated with the 6 minute walk test. During the 6 minute walk test, a participant may experience difficulty with breathing, shortness of breath, chest pains, dizziness, and/or light headedness. There is also the potential risk of a fall during the 6 minute walk. The study investigators, including the medical oncologist co-investigator, and the study team will take all precautions possible to avoid and minimize these risks (e.g., checking blood pressure and other contraindications prior to conducting test, making test optional). Should any of these occur, appropriate emergency care (e.g., 911) will be provided. A defibrillator is

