available at the ABMT Clinic, and so are nursing and other medically trained staff. Over the course of the intervention, participants will be asked to participate in in-person/in-clinic activity coaching sessions led by a certified, senior level occupational therapist and to continue this activity and skills practice on their own at home. While we do not anticipate any adverse events and the intervention is consistent with physical activity recommendations, participants may be at risk for adverse events related to physical activity such as injuries/falls, lymphedema flares, hypotension or hypoglycemia, and cardiovascular events. Again, we will obtain physician clearance for activity prior to initiating the intervention sessions and should any of these adverse events occur, appropriate emergency care (e.g., 911) will be provided. Overall, the benefits of the intervention outweigh the risks and the activity coaching component is consistent with recommendations from HCT oncology providers, occupational therapists specializing in HCT care, and national guidelines for HCT patients.

Potential Benefits and Importance of Information to be Gained. This study has several potential benefits. First, hematopoietic stem cell transplant patients with pain, fatigue, and psychological distress who participate in the intervention may learn ways to enhance their symptom coping strategies and increase their physical activity. Intervention participants may experience significant decreases in symptom severity and physical disability as well as increases in physical and psychological functioning. Second, if the proposed HCT Symptoms and Steps protocol proves to be feasible, acceptable, and shows promise for efficacy, it could be applicable to a number of patient populations with a similarly high symptom burden who face challenges similar to hematopoietic stem cell transplant patients with pain, fatigue, and distress. Third, the proposed model of intervention delivery has the potential to be expanded to intervene on a number of other needs faced by patients with chronic illness (e.g., medication adherence, caregiver burden). The proposed intervention model has the potential to dramatically redesign existing modes of behavioral intervention delivery, improve continuity and coordination of care, and improve patient outcomes.

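### Low priority: the plan allows the occupational therapist who coaches the intervention arm to run the 6-minute walk test, and nothing in the available text separates the two roles or masks the tester

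*Combined protocol and SAP*

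**What the plan says.** The Risk/Benefit Assessment places a walking test at the study assessments and states: "Study staff (e.g., CRC, Occupational Therapist) will complete the 6 minute walk test". The list of testers is open and gives examples only. The Randomized Controlled Trial paragraph has two assessments, before and after treatment.

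The coaching role is described in three places. Under Therapist Training: "Activity coaching sessions will be delivered by an OT with expertise working with HCT patients". The Risk/Benefit Assessment says that "the activity coaching sessions will be led by a senior level occupational therapist at Duke University Hospital" and later refers to "in-person/in-clinic activity coaching sessions led by a certified, senior level occupational therapist". Coaching belongs to the intervention: "HCT Symptoms and Steps will provide patients with cognitive behavioral coping skills training and activity coaching sessions". No text gives it to the HCT Education arm.

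On the amount of contact, Methodological Features says: "The initial HCT Symptoms and Steps coping skill (1) and activity coaching (2) sessions will be in-person in the hospital". Later sessions are by video. The temporary COVID-19 amendment changes this: "Session 1-3 will now be conducted via telephone or video-conferencing, the same way as the approved session 4-7".

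Aim 3 names two measures of physical disability, self-report and the walk test, and Methodological Features presents the walk test as the objective one. The Aim 3 analysis takes each person's change score, subtracts the HCT Education mean from the HCT Symptoms and Steps mean, and divides by the pooled SD of change.

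**The concern.** A walk test depends on effort, and the tester can influence effort. Apart from the walk test, the only OT work the text describes is designing and delivering the coaching, so naming an OT as a possible tester leaves open that a coach measures the outcome in patients he or she has coached. Only one arm has a coach, so any effect of that relationship falls on one arm.

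Baseline is by definition before treatment, so familiarity from coaching is present at the second test and absent at the first. Subtracting baseline therefore does not remove it. The quality procedures listed for the trial (manual, supervision, recording, adherence ratings) cover delivery of treatment, not measurement of outcome.

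At stake is the Aim 3 effect size for the only disability measure that is not self-reported. The error would be directional, so a larger sample would not average it out.

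**Working it through.** The plan states no figure on this point, so there is none to reproduce. The check has a textual part and a scale part.

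**Text, side by side**

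- Tester: study staff, with CRC and Occupational Therapist as examples (Risk/Benefit Assessment).
- Coach: an OT (Therapist Training; Risk/Benefit Assessment, twice).
- Rule separating the two, masking of the tester, or record of who tested: none found in the available text, including the Aim 2 and Aim 3 analysis paragraphs and the COVID-19 amendments.

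**Inputs**

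- N = 40 in equal allocation, so n = 20 per arm.
- Attrition limit 20%, so n = 0.8 x 20 = 16 per arm at the limit.
- f = share of intervention-arm patients whose post-treatment test is run by the coach. Not in the documents; range 0 to 1.
- b = familiarity effect on walk distance in a coached patient tested by the coach, in SDs of the change score. Not in the documents.

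**Familiarity effect.** A fraction f of the intervention arm has its change score moved by b, and no one in the HCT Education arm has been coached. So:

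shift in d = f x b - 0 = f x b (approximately, ignoring any small change in the SD).

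**General tester effect.** Let g be the OT-versus-CRC difference in technique or usual encouragement. Let p and q be the shares of an arm tested by an OT after and before treatment. The arm's mean change moves by g x (p - q), so:

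shift in d from g = g x [(p - q) in the intervention arm - (p - q) in the education arm].

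This is zero if each patient has the same tester at both visits, and also if switching is equal in the two arms. It matters only if the tester changes between visits and does so differently by arm.

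**Standard error of d near zero.** SE = sqrt(2/n).

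- n = 20: sqrt(0.100) = 0.316
- n = 16: sqrt(0.125) = 0.354

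**Break-even values for the familiarity effect**

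| | n = 20 per arm | n = 16 per arm |
|---|---|---|
| f x b equal to half an SE | 0.158 | 0.177 |
| f x b equal to one SE | 0.316 | 0.354 |
| b needed for half an SE if f = 1 | 0.158 | 0.177 |
| b needed for half an SE if f = 0.5 | 0.316 | 0.354 |
| Shift if f = 0 | 0 | 0 |

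**Effect on total error at n = 20.** Relative increase in root mean squared error = sqrt(1 + (shift/SE)^2) - 1.

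- shift 0.05: sqrt(1 + 0.025) - 1 = 1.2%
- shift 0.10: sqrt(1 + 0.100) - 1 = 4.9%
- shift 0.20: sqrt(1 + 0.400) - 1 = 18.3%

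The shifts are illustrative.

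**The case against.** The strongest case against is that this is only a possibility. The sentence comes from a safety paragraph, offers examples of staff, and is not specific to the RCT; user testers also complete assessments before and after treatment, and with a single group no bias between arms can arise. The available text also has no section describing the outcome measures (the CSQ, for instance, is used under Aim 2 without description), so a rule on testers may sit elsewhere. All of this stands. It limits the weight of the point, but the permission is still in the text.

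The consequences are also modest. The test is optional and has contraindications, so the number tested may be below 16 per arm, which enlarges the SE and makes any given shift smaller beside it. The Aim 3 paragraph itself disclaims efficacy conclusions, and no Aim 2 criterion uses walk distance. Daily steps from the tracker need no assessor and give a related cross-check, subject to the temporary suspension of Fitbit provision. Coaching partly or wholly by phone or video may leave the coach less familiar with the patient. These facts support a low priority.

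A reader might infer three stronger things that the documents do not support.

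- That the coach will be the tester. The text does not say that they are the same person, or that an OT runs any post-treatment test.
- That ordinary differences between an OT and a CRC as testers bias the comparison. They cancel within person if the tester is the same at both visits, and nothing says that testers switch, or switch differently by arm.
- That knowledge of allocation acts only after treatment. Randomization follows consent and the baseline assessment is at the first appointment after consent, but their order is not given. If allocation were known at baseline, any stable part of that effect would cancel in the change score. Only familiarity gained through coaching clearly comes later.

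**Conclusion.** The point holds as a low-priority, inexpensive improvement. The plan permits a coach to measure the walk outcome in his or her own patients, and the available text contains no safeguard. If that happens, the Aim 3 effect size for the walk test shifts by about f x b.

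The size cannot be estimated from the documents, because neither f nor b is given. At 20 per arm the shift reaches half a standard error only when f x b is about 0.16, for example b = 0.32 with half the intervention arm tested by the coach. Below that, sampling error dominates. If the coach tests none of the coached patients, the shift is zero. This rests on three assumptions: coaching is confined to the intervention arm, familiarity is absent at baseline, and the SE approximation applies at 16 to 20 per arm.

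It would be wrong to conclude that the Aim 3 result is invalid or that feasibility is affected.

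**What to change.** In the walk-test paragraph of the Risk/Benefit Assessment, state for the RCT that:

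- walk tests before and after treatment, in both arms, are run by the CRC or other existing staff who deliver no intervention sessions;
- one fixed script is used;
- the same tester sees a patient at both visits, and is not told the arm, where feasible;
- the person who ran each test is recorded;
- if no such person is available, the test is done anyway and the tester recorded, so that no assessment is lost.

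Covering both visits matters. Restricting only the post-treatment tester could itself create tester switches and put general tester differences into the change scores. The safety checks in that paragraph are untouched.

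The cost is a few sentences, one recorded field and slightly less scheduling flexibility. The CRC role is already named there, though the documents do not give CRC numbers or availability. Masking will be incomplete, since patients know their arm and the tester may learn it, so the bias is reduced, not eliminated.

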#### **Costs to the Subject**

• Describe and justify any costs that the subject will incur as a result of participation; ordinarily, subjects should not be expected to pay for research without receiving direct benefit.

There are no costs to the subject other than the time that is required to participate in the study.

#### **Data Analysis & Statistical Considerations**

Describe endpoints and power calculations. Provide a detailed description of how study data will be
analyzed, including statistical methods used, and how ineligible subjects will be handled and which
subjects will be included for analysis. Include planned sample size justification. Provide estimated time
to target accrual and accrual rate. Describe interim analysis including plans to stop accrual during
monitoring. Phase I studies, include dose escalation schema and criteria for dose escalation with
definition of MTD and DLT.

